## **11.4. Notification of Adverse Events**

### **Sponsor Notification:**

The investigational center staff must report all reportable AEs to Medtronic in a timely manner. All Severe Hypoglycemia, DKA, SAE, and SADE should be reported as soon as possible (desired within 24 hours of investigator or study coordinator awareness) to Medtronic. For the previously mentioned events, the AE eCRF will be completed with all known details as soon as possible, this will serve as notification to Medtronic. If the study database cannot be accessed due to technical problems, contact the sponsor via email at [[contact]](mailto:[contact]) and provide the known details of the event. Once the access issue has been corrected, the event should be entered onto an AE eCRF.

Source documents that support the event (e.g. clinic notes, hospital admission and discharge records, lab reports, EMT reports, ER/Urgent Care) should be provided to the sponsor via the Medtronic BOX safety folder. All source documents/medical records should be redacted of patient identifiers (full name, address, etc.) prior to providing to the sponsor. Each source page should be identified with the subject ID.

## **11.5. Expedited Safety Reporting Requirements**

For device studies, investigators are required to submit a report of a UADE to the sponsor and the reviewing IRB as soon as possible, but in no event later than 10 working days after the investigator first learns of the event (812.150(a)(1)).

The sponsor will notify the investigator and IRB of any event that results in a safety report per regulations to the FDA. Documentation of IRB notification of any safety event must be kept at the investigational center and a copy sent to the sponsor.

***It is the responsibility of the investigator to follow their IRB reporting requirements.***

## **11.6. Causality Assessment**

An AE is not automatically related to the study device or procedure simply because the subject is wearing the device and participating in the study. The event should be reviewed to determine if the device or study procedure could have possibly caused the event and therefore is related to the study device or procedure.

Causality assessment is the determination of the relationship between an AE and the device being studied. It is expected that the investigational center will review all elements surrounding the AE to properly assess the causality of the event to the study device or to a study procedure.

This review would include the subjects' description of the event, study device uploads and medical records (if applicable) from the treating facility. These records will be made available to sponsor.

Investigators should classify the relationship between the AE and the study device or study procedures using one of the five possible causality categories listed below:

- **Not related:** relationship to the device or procedures can be excluded when:
  - the event is not a known side effect of the product category the device belongs to or of similar devices and procedures
  - the event has no temporal relationship with the use of the investigational device or the procedures;
  - the event does not follow a known response pattern to the medical device (if the response pattern is previously known) and is biologically implausible;
  - the discontinuation of medical device application or the reduction of the level of activation/exposure - when clinically feasible – and reintroduction of its use (or increase of the level of activation/exposure), do not impact on the serious event;
  - the event involves a body-site or an organ not expected to be affected by the device or procedure;
  - the event can be attributed to another cause (e.g. an underlying or concurrent illness/ clinical condition, an effect of another device, drug, treatment or other risk factors);
  - the event does not depend on a false result given by the investigational device used for diagnosis, when applicable;
  - harms to the subject are not clearly due to use error;
  - In order to establish the non-relatedness, not all the criteria listed above might be met at the same time, depending on the type of device/procedures and the serious event.
- **Unlikely:** the relationship with the use of the device seems not relevant and/or the event can be reasonably explained by another cause, but a relationship to the device cannot be completely ruled out.
- **Possible:** the relationship with the use of the investigational device is weak. Alternative causes are also possible (e.g. an underlying or concurrent illness/ clinical condition or/and an effect of another device, drug or treatment). Cases where relatedness cannot be assessed should also be classified as possible.
- **Probable:** the relationship with the use of the investigational device seems relevant and/or the event cannot reasonably be explained by another cause.
- **Causal relationship:** the event is associated with the investigational device or with procedures beyond reasonable doubt when:
  - the event is a known side effect of the product category the device belongs to or of similar devices and procedures;
  - the event has a temporal relationship with investigational device use/application or procedures;
  - the event involves a body-site or organ that
    - the investigational device or procedures are applied to;
    - the investigational device or procedures have an effect on;
  - the event follows a known response pattern to the medical device (if the response

- pattern is previously known);
- the discontinuation of medical device application (or reduction of the level of activation/exposure) and reintroduction of its use (or increase of the level of activation/exposure), impact on the event (when clinically feasible);
- other possible causes (e.g. an underlying or concurrent illness/ clinical condition or/and an effect of another device, drug or treatment) have been adequately ruled out;
- harm to the subject is due to error in use;
- the event depends on a false result given by the investigational device used for diagnosis, when applicable;
- In order to establish the relatedness, not all the criteria listed above might be met at the same time, depending on the type of device/procedures and the serious event.

**Example: A severe hyperglycemia AE with the following event description would have the following causality assessment for device relatedness:**

Improved glucose without an infusion set/site change	Not related
Changed infusion set with glucose improvement	Possible
Infusion set fell out, bent cannula, occlusion alarm	Causal relationship

## 11.7. Anticipated or Unanticipated

If an AE is determined to be related to the study device, the sponsor will then assess the event to determine if it is anticipated or unanticipated.

- **Anticipated:** the event is identified in the CIP; labeling; report of priors/ Investigator's Brochure (IB) or user guide.
- **Unanticipated:** the event has not been previously identified in the CIP; labeling; report of priors/IB or user guide.

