## 9.12. Stopping Rules for Entire Study

During the study period, the following steps will be taken for:

- Unanticipated Adverse Device Effects (UADE)
- Algorithm-related Diabetic Ketoacidosis (DKA)
- Algorithm-related Severe hypoglycemia

1. Site will notify the sponsor within approximately 24 hours of receiving knowledge of the event.
2. Sponsor will notify Food and Drug Administration (FDA) within approximately 72 hours of knowledge of the event and provide updates to those agencies as information becomes available.
3. Clinical Events Committee (CEC) is to review the event within 10 days from the time that the sponsor is notified.
4. CEC will provide recommendation to the sponsor on the following:
  - a) If enrollment and study may continue
  - b) If enrollment should be stopped; enrolled subjects are still allowed to continue in study
  - c) If the entire study must be stopped, including subjects who have already received study devices
5. The study will be suspended if 2 or more algorithm-related DKA events OR 4 or more algorithm-related Severe Hypoglycemia events occur

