
Risks with the use of an insulin infusion pump may include the risk of malfunction of the components of the system (pump, software, infusion set and reservoir) as well as the risk of use error during use of the system. Device deficiencies or use errors can result in administration of too much or too little insulin which can lead to the following clinical consequences:
 

• Hypoglycemia

• Hyperglycemia

• Diabetic ketoacidosis

• Severe hypoglycemia with or without associated seizure, coma or death

• Kinked cannula leading to hyperglycemia

• Infusion set disconnection from pump leading to hyperglycemia

• Subject removes the reservoir from the pump but forgets to disconnect the infusion set from the body which results in hypoglycemia or severe hypoglycemia

• Dislodged cannula leading to hyperglycemia

• A pump error may lead to under delivery or over-delivery of insulin

• Battery failure – no insulin delivered

	
Prevention and mitigation include:
 

• Follow the provided user guides& instructions for insulin pump management which includes information on infusion set change.

• Train prior to study device use on appropriate device use and diabetes management principles and instruct to call investigator with problems.

• Check SMBG 4-6 times a day and also before driving (as applicable).

• Instruct to have glucose on hand for hypoglycemia

• Instruct to change infusion set if suspected catheter occlusion or administer insulin with syringe for persistent hyperglycemia especially if ketones develop.

• Parent(s)/guardian(s)/companion(s) will be present at night with subjects and will be trained on study device and diabetes management principles and instructed to call investigator with problems.

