### **Unanticipated Adverse Device Effect (UADE) (21 CFR 812.3(s))**

Any serious adverse effect on health or safety or any life-threatening problem or death caused by, or associated with, a device, if that effect, problem, or death was not previously identified in nature, severity, or degree of incidence in the investigational plan or application (including a supplementary plan or application), or any other unanticipated serious problem associated with a device that relates to the rights, safety, or welfare of subjects.

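### Section 11.7 omits the severity and incidence tests of the UADE definition in 11.2, so some serious device-related harms named in Table 6 could be classed as anticipated and miss the UADE trigger in 9.12

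*Protocol*

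**What the plan says.** Two parts of the protocol bear on whether a device-related event was expected.

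- **Section 11.2, UADE definition (after 21 CFR 812.3(s)).** The event must be serious: "Any serious adverse effect on health or safety or any life-threatening problem or death caused by, or associated with, a device". It must also be "not previously identified in nature, severity, or degree of incidence in the investigational plan or application". Novelty in any one of the three attributes is enough. A closing clause adds other unanticipated serious problems tied to a device.
- **Section 11.7.** Once an AE is judged device-related, "the sponsor will then assess the event to determine if it is anticipated or unanticipated". Anticipated means that "the event is identified in the CIP; labeling; report of priors/ Investigator's Brochure (IB) or user guide". Unanticipated means that "the event has not been previously identified in the CIP; labeling; report of priors/IB or user guide".

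Section 9.12 starts a set of steps for three kinds of event: a UADE, algorithm-related DKA and algorithm-related severe hypoglycemia. The steps are site notice to the sponsor in about 24 hours, sponsor notice to FDA in about 72 hours, CEC review within 10 days, and a CEC recommendation on whether enrollment and the study go on. The study is suspended at 2 or more algorithm-related DKA events or 4 or more algorithm-related severe hypoglycemia events.

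Table 6 names many serious harms, among them "Severe hypoglycemia with or without associated seizure, coma or death". The SAP's safety evaluation (7.10) does not address this classification.

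**The concern.** Section 11.7 is the step at which the sponsor labels each device-related event, and it asks only whether the event has been mentioned somewhere. The protocol's own definition of a UADE also asks whether the event is worse, or more common, than was foreseen. The two tests give different answers for the same event, and neither section says which one governs.

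UADE status is the only way into 9.12 for a serious device-related harm that is not algorithm-related DKA or severe hypoglycemia. If the sponsor decides that status by 11.7, a run of such harms could accumulate without starting the formal steps. Section 10.4 describes the study's primary risk as a possible increase in hypoglycemia, which is a question of how often events occur and not of whether they are listed. The sponsor rates the study as significant risk (10.5), and it admits children from age 2.

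**Working it through.** No arithmetic applies. The check sets the sections side by side and traces which events reach 9.12.

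1. **Attributes tested.** Section 11.2 tests nature, severity and degree of incidence. Section 11.7 tests only whether the event is identified. Take a serious device-related harm that Table 6 already names but that occurs in a graver form or more often than foreseen. It can be a UADE under 11.2, and it is anticipated under 11.7.

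2. **Sources consulted.** Section 11.2 looks to the investigational plan or application. Section 11.7 also accepts labeling and user guides. Labeling is supplied separately (18.2) and the application is not among the documents, so whether this widens the list in practice cannot be judged here.

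3. **Routes into 9.12.**

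| Event | Route into 9.12 | Does 11.7 matter? |
|---|---|---|
| Algorithm-related DKA or severe hypoglycemia | Own trigger, from the first event; suspension at 2 or 4 | No |
| Other serious device-related harm named in Table 6 | UADE only | Yes: anticipated at any severity or count if 11.7 is read literally |
| Serious device-related harm named in none of the listed sources | UADE | No: new under both tests |
| Non-serious device-related harm | Generally none | No: 11.2 already leaves it out for lack of seriousness |

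   Only the second row is exposed.

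4. **Example.** Suppose a pump malfunction causes severe hypoglycemia or DKA. Table 6, under insulin administration and pumps, names pump error and both outcomes. Section 12.1 tells the CEC that either outcome, if directly caused by a device malfunction, might stop enrollment or the whole study. Without algorithm causation the event enters 9.12 only as a UADE. By 11.7 it is anticipated the first time and every later time. A concern that 12.1 treats as able to stop the study may therefore not start the stopping steps.

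5. **Benchmark.** Table 6 lists harms without numerical rates. Even under 11.2, the protocol gives no figure against which the sponsor could judge incidence. The report of priors or the application may hold one, but the protocol does not point to it for this purpose.

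6. **What would be lost.** The early site notice largely survives, because 11.4 asks for severe hypoglycemia, DKA, SAEs and SADEs as soon as possible, ideally within 24 hours. The 72-hour FDA notice, the 10-day CEC deadline and the formal recommendation on continuing belong to 9.12 and would not be started.

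**The case against.** A reader might infer that an excess of any harm named in Table 6 can never become a UADE or start the stopping steps. The documents do not support that, for three reasons.

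- Algorithm-related DKA and severe hypoglycemia are in Table 6 and start 9.12 from the first event, with suspension counts and no condition that they be unanticipated. They are the harms most closely tied to the algorithms under test.
- Section 11.7 does not mention UADEs and does not say that it replaces 11.2. The 9.12 trigger uses the defined term, and 11.2 adopts the 21 CFR 812 definitions. Section 11.5 obliges investigators to report UADEs whatever label the sponsor applies. A sponsor who applies 11.2 would still classify correctly.
- Other safeguards do not depend on 11.7. The CEC reviews every SAE, SADE, severe hypoglycemia, DKA and severe hyperglycemia, and may consider whether an event was unanticipated (12.1). The Data Monitoring Committee can meet ad hoc (12.2). The sponsor or a regulator may suspend the study if risk proves higher than indicated (16.10).

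Section 12.1 also says that DKA caused directly by an infusion set, with the pump working as intended, would probably not stop the study. That example is a deliberate choice and should not be counted against 11.7.

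All of this stands, and it narrows the point without removing it. An excess spread over up to 15 centers is visible to the sponsor rather than to any one investigator, and 11.7 gives the classification to the sponsor. The CEC's look at anticipation is optional, and its 10-day clock runs only under 9.12. Ad hoc meetings and 16.10 carry no count or deadline.

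**Conclusion.** The inconsistency is real and worth correcting, but its reach is limited. Followed literally, 11.7 gives a different safety classification from the protocol's own UADE definition for one class of event: serious device-related harms that are already named and that are not algorithm-related DKA or severe hypoglycemia. For that class, the 72-hour FDA notice, the 10-day CEC review and the CEC's recommendation on continuing are at risk. Sponsor awareness and CEC review as such are not.

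The conclusion assumes that the sponsor would use 11.7 to decide UADE status. The text permits this but does not state it. No numerical size can be given: the documents contain no background rates for these events, and a figure built on assumed rates would reflect only the assumptions.

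**What to change.** Reconcile 11.7 with 11.2. For serious device-related events, have the sponsor judge nature, severity and degree of incidence against the investigational plan or application, and state that being mentioned in a document is not sufficient to make an event anticipated. State, or give a reference for, the expected severity and incidence used as the benchmark. Have the sponsor record this judgment, with the cumulative count, for each serious device-related event.

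The cost is about two sentences in 11.7 and one field on the sponsor's assessment form, plus the benchmark or a reference to it. No visit, treatment or endpoint changes. The downside is that a few more events may go through the 9.12 steps.

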## 12. Data Review Committees

### 12.1. Clinical Events Committee

A clinical events committee (CEC) consisting of external physicians with an expertise in endocrinology and the management of diabetes including insulin pumps and CGM will be convened. The CEC will review AEs as required per protocol, which include reports of:

- Serious Adverse Event
- Serious Adverse Device Effect
- Unanticipated Adverse Device Effect
- Severe Hypoglycemia
- Diabetic Ketoacidosis
- Severe Hyperglycemia

The CEC will assess events to determine agreement or disagreement with the investigator classification of an event. The CEC will only provide three causality assessments for device and procedure relatedness: Not Related, Possible, and Causal relationship.

If the CEC disagrees with the investigator's classification of the event, the rationale will be provided to the investigator. If the investigator agrees with the CEC's adjudication, the CRF documenting the AE will be updated accordingly.

If the investigator does not agree with the CEC's adjudication classification, both determinations will be provided within the final report; however, the CEC's adjudication will be used for data analysis. The disagreement will also be included in reporting to ECs and regulatory authorities, if required.

Causality Categories for Investigational Center	Causality Categories for CEC:

• Not Related

• Unlikely

• Possible

• Probable

• Causal relationship

	

• Not Related

• Possible

• Causal relationship

The sponsor will notify the investigator of any disagreement in assessment of an event by the CEC.

Refer to Section 9.12 for Stopping Rules for Entire Study and 10 day review requirements.

The CEC may review applicable information for device related AEs which may include:

- Whether or not the event was unanticipated
- Review of sensor data from CareLink™ Personal For Clinical Research software report (when applicable)
- Review of pump data from CareLink™ Personal For Clinical Research software report (when applicable)
- Misuse of the device by the user

Review of events may require the following information. Final disposition may be delayed based on obtaining this information:

- Monitoring by sponsor at site
- Device return and failure analysis
- CareLink™ Personal For Clinical Research upload and review of CareLink™ Personal For Clinical Research software reports
- Subject clarification to site regarding details about the event

- Source documents that support event: Paramedic records; ER records; Lab records; Hospital admission and discharge summary

The following factors should be carefully considered in the CEC's recommendation to sponsor:

1. Was the severe hypoglycemia or DKA related to the AHCL algorithm, or was it related to a known insulin pump risk? For example, a question that may be considered in DKA would be whether the event was related to an infusion set issue or caused by the AHCL algorithm.
2. Another important consideration would be if the severe hypoglycemia, severe hyperglycemia or DKA event was related to a device malfunction versus patient non-compliance. For example, if a software anomaly leading to an under-delivery of insulin is discovered versus the subject repeatedly ignoring alarms prompting the subject to take action.
3. Severe hypoglycemia, severe hyperglycemia or DKA caused directly by an infusion set issue when the study pump is functioning as intended would likely result in acceptance to proceed with the study versus severe hypoglycemia or DKA that are directly caused by the AHCL algorithm or a device malfunction might stop study enrollment or entire study altogether.
4. It should be noted that the final determination of causality related to AHCL System that is made by the CEC may include additional factors which the members consider to be clinically relevant and important.

## **12.2. Data Monitoring Committee**

A data monitoring committee (DMC) consisting of external physicians with an expertise in Endocrinology and the management of insulin-requiring diabetes including CGM, along with an external statistician will be convened to review study safety. The Board will also meet when ad hoc review is required.

The DMC will review Safety data and provide a recommendation to the sponsor regarding staged enrollment of pediatric subjects:

- Enrollment of pediatric subjects 2-13 years of age into a specific phase may not proceed until N=10 subjects 14 years and older have completed the corresponding phase and safety data has been reviewed by the DMC.
- Study subjects 2-6 years of age will be enrolled in Cohort A and Cohort C only after completing an in clinic observational study using the AHCL system and safety data has been reviewed by the DMC.
- DMC will review in clinic data from subjects in the 5-6 year age group (N=8), in order to assess that it is safe for 5-6 year olds to perform Cohort A or Cohort C study procedures.
- DMC will review in-clinic data from both the 2-4 year age group (N=8) and the 5-6 year age group (N=8) in order to assess that it is safe for 2-4 year olds to perform Cohort A and Cohort C study procedures.

